	
 
c. Hepatic, renal, neurological, or metabolic conditions - which in the opinion of the Investigator would compromise the protocol objectives
 
d. Psychiatric conditions e.g. patients unlikely to comply with the protocol, e.g. mental condition rendering the patient unable to understand the nature, scope, and possible consequences of participating in the study
 
e. History of erythema multiforme, toxic epidermal necrolysis or Stevens-Johnson syndrome
 
f. Cardiac conditions, including: 
 
i. history of acute coronary syndromes (including unstable angina)
 
ii. class II, III or IV heart failure as defined by the New York Heart Association (NYHA) functional classification system
 
iii. known uncontrolled arrhythmias (except sinus arrhythmia) in the past 24 weeks
 
 
 

Sample size	6 to 12 patients will be enrolled
Treatment groups, dose, route of administration, treatment regimen	Single arm study with patients to be treated with the following study drugs: Rituximab - 375 mg/m  to be administered by i.v. infusion through dedicated line at Days -14, 7, 14, 21 and 28. Patients who achieve SD, CR or PR on their Month 3 imaging scan will be administered maintenance RTX 375 mg/m  i.v. or 1400 mg s.c. every 3 months for up to 2 years (8 infusions in total), or until disease progression or withdrawal from the study for any other reason (whichever comes first).
	Lilotomab – 40 mg to be administered by i.v. infusion at Day 0
	Betalutin – 10 or 15 MBq/kg to be administered by slow bolus i.v. injection within 4 hours following lilotomab on Day 0
Efficacy assessment(s)	PET/CT and CT (or MRI) imaging will be performed at baseline and then at 3 and 6 months. CT with contrast (or MRI) will be performed at 12, 18, 24 months or until disease progression or withdrawal from the study for any other reason (whichever comes first)  Tumour response will be determined locally according to Recommendations for Initial
	Evaluation, Staging and Response Assessment of Hodgkin and non-Hodgkin Lymphoma [Cheson, 2014]
Safety assessment(s)	In the treatment phase vital signs, electrocardiogram (ECG), physical examination, haematology, serum biochemistry and all AEs are collected at specified time points.

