#### All blood samples at each visit to be taken before study drug administration (unless specified)

1) Define absolute cell counts for peripheral blood T-cells, CD4 T-cells, CD4 T-cells, B-cells and NK cells, respectively identified as CD3+, CD3+CD4+, CD3+CD8+, CD19+ and CD3- CD16+ CD56+ lymphocytes, by flow cytometry.

- 2) A serum sample will be sent for HAMA screening to a central laboratory (mandatory). Eligibility can be assessed using a local test such as the Milenia Quickline® HAMA test (optional).
- 3) Assessment of anti-drug antibodies directed against lilotomab, Betalutin and/or RTX.
- 4) CD37 and CD20 expression in tumour will be assessed by immunohistochemistry. Prior to treatment, an archived tumour tissue biopsy (FFPE block) can be used. If not available, a new tissue biopsy to be collected surgically at screening.

A new turnour tissue biopsy (optional) will be collected surgically at relapse and /or disease progression. Preparation of the 5 µM FFPE slides for the analysis will be performed only when requested by Sponsor.

Note: A sample of the archived or newly collected tumour tissue biopsy will be used to calibrate the blood MRD test (see footnote 10). A biopsy sample may also be used for the optional gene expression analysis in tumour (see footnote 5).

- 5) Optional, A sample of an archived or new tissue biopsy collected prior to treatment, at relapse and/or disease progression can be used (see footnote 4). Preparation of the 5 µM FFPE slides for the analysis only when requested by Sponsor.
- 6) Optional, HLA-typing. Blood sample preferred or alternatively a saliva sample either direct or via mouth swab may be taken.
- 7) Optional, to be performed at Radium Hospital (Oslo, Norway) only. Additional tumour tissue biopsy (surgical) to explore the anti-tumour T-cell response.
- 8) Optional, to be performed at Radium Hospital (Oslo, Norway) only. Additional tumour tissue biopsy (fine needle aspiration) to explore the anti-tumour T-cell response.
- 9) Optional, to be performed at Radium Hospital (Oslo, Norway) only. Additional peripheral blood samples to explore the anti-tumour T-cell response.
- 10) A sample of an archived tumour biopsy collected before treatment or a new tumour tissue biopsy collected at screening will be used to calibrate the blood MRD test (see footnote 4). Preparation of the 5 µM FFPE slides for the analysis only when requested by Sponsor.
- 11) FDG PET/CT Imaging and Contrast CT or MRI

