#### 5.1. Inclusion Criteria

Patients are eligible to be included in the study only if all of the following criteria apply:

- 1) Patient must be  $\geq$ 18 years at the time of signing the informed consent
- 2) A pre-study Eastern Cooperative Oncology Group (ECOG) performance status of 0-2
- 3) Histologically confirmed diagnosis (by 2008 World Health Organization [WHO] classification) of indolent non-Hodgkin B-cell FL (grade 1, 2 or 3a)
- 4) At least one (but not more than 3) prior regimens with an anti-CD20 antibody (alone or in combination with chemotherapy), with documented relapsed, refractory disease (must not be anti-CD20 antibody-refractory) or PD
- 5) Presence of at least one bi-dimensionally measurable lesion by CT or MRI: longest diameter (LDi) >1.5 cm for a nodal lesion; LDi >1.0 cm for an extranodal lesion within 28 days prior to start of treatment
- 6) Normal organ and bone marrow function defined as:
  - a. Absolute neutrophil count  $\geq 1.5 \times 10^9/L$ ;
  - b. Platelet count  $\geq 150 \times 10^9 / L$ ;
  - c. Haemoglobin ≥9 g/dL;
  - d. Total bilirubin ≤1.5 x upper limit of normal (ULN) (except patients with documented Gilbert's syndrome [<3.0 mg/dL]);
  - e. Liver enzymes: Aspartate transaminase (AST); Alanine transaminase (ALT) or Alkaline phosphatase (ALP) ≤2.5 x ULN (or ≤5.0 x ULN if liver involvement by primary disease);
  - f. Adequate renal function as demonstrated by a serum creatinine within the upper limit of normal range
- 7) Bone marrow involvement by lymphoma <25%
- 8) Life expectancy >3 months
- 9) Negative hepatitis B, hepatitis C and human immunodeficiency virus (HIV) screening tests
- 10) Undetectable human anti-murine antibody (HAMA) at screening
- 11) Women of childbearing potential (see Appendix 3) must:
  - a. have a negative serum pregnancy test at screening
  - b. understand that the study medication is expected to have teratogenic risk
  - c. agree to use, and be able to comply with, highly effective method of birth control with a Pearl-Index  $\leq 1\%$

Contraception is required without interruption, from 4 weeks before starting study drug, throughout study drug therapy and for 12 months after end of study drug therapy, even if she has amenorrhea

12) Male patients must agree to use condoms (See Appendix 3) during intercourse throughout study drug therapy and for 12 months after end of study drug therapy

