Immunophenotyping	Define absolute cell counts for circulating T-cells, CD4 T-
	cells, CD8 T-cells, B-cells and NK cells, respectively
	defined as CD3+, CD3 + CD4 + , CD3 + CD8 + , CD19+ and
0 1.1	CD3 CD16 + CD56 + lymphocytes by flow cytometry
Coagulation	International normalised ratio (INR), partial
C ' 1	thromboplastin time (PTT)
Serum virology	HIV test, Hepatitis B test (HBsAg and anti-HBc),
Dungananan tart	Hepatitis C
Pregnancy test	For women of childbearing potential: serum beta human-
Immunaglabulin layala	chorionic gonadotropin (ß-HCG) pregnancy test Quantitative serum immunoglobulins (IgG, IgA and IgM)
Immunoglobulin levels HAMA screening	To screen for pre-existing human anti-mouse antibodies.
HAMA screening	A serum sample will be sent to a central laboratory
	(mandatory). Eligibility can be assessed using a local test
	such as the Milenia Quickline® HAMA test (optional)
Immunogenicity	Monitoring ADA response (RTX, lilotomab and Betalutin
	baseline)
Tumour tissue biopsy (if no available	Assessments to be performed:
archived FFPE block, a new surgical	Mandatory: CD20 and CD37 expression in
tumour tissue biopsy will be	tumour by immunohistochemistry
performed)	Mandatory: Calibration of the blood MRD test
	Optional: Gene expression analysis in tumour
	(DNA, RNA, proteins) to evaluate the
	relationship between anti-tumour activity and
	NHL-related genes.
	Note : If FFPE block not biobanked at Covance Central
	Laboratories (CCLS), preparation of the 5μM FFPE slides
	for the respective analyses only after Sponsor request
Optional: HLA haplotyping – (saliva	Human Major Histocompatibility Complex (MHC) class
sample direct or mouth swab, only if	I/II haplotyping
not possible to collect blood sample)	
Minimal Residual Disease	MRD monitoring to assess early treatment response and
(biopsy  and peripheral blood sample)	detect relapse (baseline)
Bone marrow, biopsy	To verify <25% tumour cells in bone marrow, biopsy
D. U. I	taken from a site not previously irradiated.
Radiology - FDG PET/CT	Using standard institutional guidelines. Patient needs to be
	fasting 6 hours prior to PET/CT examination. Information
	about FDG administration and standardised uptake value
	(SUV max ) will be recorded. The same camera should
	preferably be used throughout the study.

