#### 9.2.6.4. Clinical laboratory parameters

Blood samples for the determination of haematology and serum biochemistry parameters will be drawn at pre-specified time points, as per the Schedule of activities (Section 1.2).

The following laboratory tests will be performed:

**Table 9-3** Clinical laboratory parameters

Serum Biochemistry	Haematology	Urine
Sodium	Haemoglobin	Urine pregnancy test at day 0
Potassium	Platelets	
Calcium	White blood cell count	
Creatinine	Differential	
Uric acid	Neutrophils	
Alkaline Phosphatase (total ALP)	Lymphocytes	
Aspartate aminotransferase (ASAT)	Monocytes	
Alanine aminotransferase (ALAT)	Eosinophils	
Lactate Dehydrogenase (LDH)	Basophils	
Glucose	Immunophenotyping**	
Bilirubin, total	Coagulation:	
Gamma-glutamyl transferase (GGT)	International normalised ratio	
Magnesium	(INR), prothrombin time (PTT)	
Albumin		
HIV test*		
Hepatitis B test (HBsAg and anti- HBc)*		
Hepatitis C*		
b-hCG (pregnancy test)*		
Quantitative serum immunoglobulins (IgG, IgA and IgM)		
HAMA at screening*		

\* A serum sample will be sent for HAMA screening to a central laboratory (mandatory). Eligibility can be assessed using a local test such as the Milenia Quickline® HAMA test (optional). If the Milenia Quickline® HAMA test is positive, eligibility can only be assessed using the results from the central laboratory.

Reference ranges from the laboratory will be provided to the Sponsor. If during the study, ranges should be changed, the Investigator is requested to provide updated laboratory normal values.

The Investigator will interpret all clinical laboratory test results outside the reference range, using the following criteria:

- 1 = Value out of reference range, but not a clinically significant worsening from previous examination.
- 2 = Value out of reference range, and a clinically significant worsening from previous examination.

\*\*Absolute cell counts for circulating T-cells, CD4 T-cells, CD8 T-cells, B-cells and NK cells, respectively defined as CD3+, CD3+CD4+, CD3+CD8+, CD19+ and CD3-CD16+CD56+ lymphocytes by flow cytometry. At certain time points specified in Schedule of activities (Section 1.2).

CONFIDENTIAL

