#### 9.2.6.5. Immunogenicity assessment

#### 9.2.6.5.1. Assessments

Immunogenicity i.e. development of ADAs is of concern as ADA can reduce the efficacy of the therapeutic protein but also, in some specific cases, impact on patient safety [36-38].

In this study, the immunogenicity risk for the patient is related to the immunogenicity potential of (1) lilotomab, (2) the chemical linker p-SCN-Bn-DOTA (satetraxetan), and (3) RTX. The immunogenicity potential of ARC using satetraxetan is suggested to be dependent of the carrier molecule rather than DOTA itself [39]. RTX immunogenicity has been reported but without a demonstrated clinical relevance [40-42]. Therefore, immunogenicity assessments for ADA monitoring will be focused on lilotomab and RTX as follow:

- Monitoring of the ADA response after injection of lilotomab/Betalutin according to a tiered approach (https://www.fda.gov/downloads/Drugs/Guidances/UCM192750.pdf), using a bridging assay format
- Monitoring of the ADA response after RTX dosing, before during and after combination with Betalutin. A commercial kit will be used for this assessment.
- HLA class II haplotype of the patients [43] (see section 9.4).

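### A negative optional local HAMA test can settle eligibility, and nothing requires the mandatory central result before dosing or says that it governs inclusion criterion 10

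*Combined protocol and SAP*

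**What the plan says.** Criterion 10, in the synopsis and in Section 5.1, is unqualified: "Undetectable human anti-murine antibody (HAMA) at screening". It names no assay, cut-off or deciding laboratory.

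Three places describe the test: footnote 2 to the Schedule of Activities (Section 1.2, Table 1-1), Table 8-1 (Section 8.1) and the footnote to Table 9-3 (Section 9.2.6.4). Table 8-1 gives the purpose: "To screen for pre-existing human anti-mouse antibodies". All three have the same two elements:

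- A central sample for everyone: "A serum sample will be sent for HAMA screening to a central laboratory (mandatory").
- An optional local route to eligibility: "Eligibility can be assessed using a local test such as the Milenia Quickline® HAMA test (optional").

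Only the Table 9-3 footnote adds a third: "If the Milenia Quickline® HAMA test is positive, eligibility can only be assessed using the results from the central laboratory".

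The Introduction (Section 2) describes lilotomab, the antibody in Betalutin, as murine. Section 9.2.6.5.1 names lost efficacy and, in some cases, effects on safety as the reasons why antibodies against the drug matter: "development of ADAs is of concern as ADA can reduce the efficacy of the therapeutic protein but also, in some specific cases, impact on patient" (quotation cut before its last word).

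**The concern.** The central result is the reference when it might rescue a patient whom the local test would exclude. It has no stated role when it might exclude a patient whom the local test has cleared. Criterion 10 exists to keep out patients with pre-existing anti-murine antibody, so the error that matters more for it is the local false negative, and that is the error left without a required check.

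The cohorts are small. Such a patient's DLT status would enter an escalation decision, and the patient would also count in the response rate, the immunogenicity results and, where sampled, the blood radioactivity profile. The protection that the criterion is meant to give that patient would also be lost.

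**Working it through.** No figure in the plan is tied to this rule, so there is none to reproduce. The check sets the provisions side by side.

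**1. Which result decides eligibility**

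| Local test | Central sample sent? | Result that decides, as written |
|---|---|---|
| Not done | Yes | Central, as the only result |
| Positive | Yes | Central only (Table 9-3 footnote; absent from Table 1-1 footnote 2 and Table 8-1) |
| Negative | Yes | Local may be used; no rule if central is later positive |

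The gap is the third row. The sample is sent in every row. What changes is which result has to be waited for.

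**2. Is there a timing requirement?** Section 8.1 places screening within 4 weeks before the first rituximab dose. That dose is on Day -14 and lilotomab on Day 0. From the screening sample to lilotomab there are nominally at most 28 + 14 = 42 days. If the sample is taken just before rituximab there are about 14, or 14 - 2 = 12 with the 2-day allowance in Table 8-2. A central result could well arrive in that time. No turnaround is stated, however, and neither Section 8.2.1 (Day -14) nor Section 8.2.2 (Day 0) lists the central HAMA result as something to confirm. Section 8.2.2 does require a negative pregnancy test before lilotomab, so the protocol uses such a check elsewhere.

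**3. Would a later step catch the patient?**

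- Section 6.1 makes a patient evaluable for dose decisions on receipt of all doses and haematological recovery. Confirmed eligibility is not a condition.
- Section 10.1.1 defines the intent-to-treat and safety populations by treatment received.
- The screening anti-drug antibody sample (Section 9.2.6.5.2) is frozen, shipped and biobanked (Section 9.2.6.5.3). It is a baseline for later comparison and is not used to decide on dosing.

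**4. Weight of one such patient.** The synopsis states that "6 to 12 patients will be enrolled".

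- Share of a DLT cohort: 1/6 = 17% to 1/3 = 33%.
- Share of the study: 1/12 = 8% to 1/6 = 17%.

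Under Section 6.1, one patient's status separates 0/3 from 1/3, or 1/6 from 2/6. Each of these pairs leads to a different next step.

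**5. Probability.** Two things must coincide: a false-negative local test, and dosing before the central result is available or acted on. The documents give no HAMA prevalence, local-test sensitivity, share of patients cleared locally or central turnaround, so no probability follows from them.

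**The case against.** The strongest reply is that criterion 10 stands on its own. Patients are eligible only if every criterion is met, so a positive central result on the screening sample means that criterion 10 is not met. The local-test sentence is permissive and does not say that a local negative overrides a known central positive. This is right, and it limits the point: the documents do not direct anyone to dose a patient known to be HAMA-positive. What remains is the case in which the central result is not yet known or not looked at, and there the documents are silent.

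A reader might draw four stronger conclusions. None is supported.

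- **That only local positives go to the central laboratory.** All three places make the central sample mandatory without condition.
- **That the central result would come too late to matter.** No turnaround is given, and the 14 to 42 nominal days may be ample.
- **That pre-existing antibody would be mistaken for a treatment-induced response.** The baseline sample at screening, together with the central HAMA result, largely allows the two to be separated.
- **That the risk can be put at some percentage.** Assume, with no source in the documents, prevalence p of 5% to 10%, local sensitivity s of 95% to 80%, and specificity 95%. The fraction positive among local negatives is f = p(1-s)/[p(1-s) + (1-p) x 0.95]. This gives 0.0025/0.9050 = 0.28% to 0.0200/0.8750 = 2.29%. The chance of at least one is 1-(1-f)^n: 1.6% to 13% for n = 6, and 3.3% to 24% for n = 12. These figures also suppose that every patient is cleared locally and that no central result arrives before dosing. They are ceilings on assumed inputs, not estimates.

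A turnaround or release rule may also exist in the laboratory manual, which is not among the documents. Which result governs an inclusion criterion still belongs in the protocol.

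**Conclusion.** The point holds in limited form. Central HAMA testing is mandatory for all, but the wording lets a negative local test suffice for eligibility. It sets no time by which the central result must be in hand, and it leaves a local-negative, central-positive patient without a rule. The rule for a positive local test appears in only one of the three places that should agree.

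The size is that of one patient in a 3-to-6-patient cohort. How likely that is cannot be derived from the documents. The conclusion rests on reading the explicit restriction after a local positive as implying its absence after a local negative, which is the natural reading. This should be corrected because it bears on patient safety and on cohort integrity. It is not evidence that any ineligible patient has been dosed.

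**What to change.** Reconcile Table 1-1 footnote 2, Table 8-1 and the Table 9-3 footnote so that they carry the same rule, for example:

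*Criterion 10 is assessed on the central laboratory HAMA result, whatever the result of any local test. The central result must be available and reviewed before lilotomab is given on Day 0. A local test may be used for planning or early screening only.*

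The sponsor may choose an earlier deadline, such as the first rituximab dose, which ends the pre-treatment period in Section 8.1. Only one deadline should be stated, since rituximab is itself a study drug and the two dates differ by 14 days.

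The documents do not say whether enrolment is still open. The first patient entered in October 2018, and the expected 18 months of accrual would have ended around April 2020, before this version of October 2021. For patients already enrolled, compare local and central HAMA results, list any local-negative, central-positive case as an eligibility deviation, and note the cohort in which that patient was counted.

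The cost is one rule in three places, a short data listing and an occasional wait for the central result. No new sample or procedure is needed.

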#### 9.2.6.5. Immunogenicity assessment

#### 9.2.6.5.1. Assessments

Immunogenicity i.e. development of ADAs is of concern as ADA can reduce the efficacy of the therapeutic protein but also, in some specific cases, impact on patient safety [36-38].

In this study, the immunogenicity risk for the patient is related to the immunogenicity potential of (1) lilotomab, (2) the chemical linker p-SCN-Bn-DOTA (satetraxetan), and (3) RTX. The immunogenicity potential of ARC using satetraxetan is suggested to be dependent of the carrier molecule rather than DOTA itself [39]. RTX immunogenicity has been reported but without a demonstrated clinical relevance [40-42]. Therefore, immunogenicity assessments for ADA monitoring will be focused on lilotomab and RTX as follow:

- Monitoring of the ADA response after injection of lilotomab/Betalutin according to a tiered approach (https://www.fda.gov/downloads/Drugs/Guidances/UCM192750.pdf), using a bridging assay format
- Monitoring of the ADA response after RTX dosing, before during and after combination with Betalutin. A commercial kit will be used for this assessment.
- HLA class II haplotype of the patients [43] (see section 9.4).

#### 9.2.6.5.2. Human biosamples collection schedule

Sampling of peripheral blood for ADA monitoring will be performed at the following approximate time points:

- Screening (Baseline for lilotomab, Betalutin and RTX ADA monitoring)
- After Betalutin administration, at Day 28 and 3, 6, 12, 18 and 24 months. It has to be noted that at Day 28, peripheral blood sampling should be done before RTX dosing.

The time points mentioned are approximate time points. The exact time point when the sample is taken needs to be recorded in the eCRF.

## 9.2.6.5.3. Human biosamples handling

A volume of approximately 6 mL of peripheral blood will be collected by venipuncture at each time point (see above and Section 1-2) to monitor the development of an ADA response post lilotomab/Betalutin treatment. Serum samples will be isolated, aliquoted and frozen on site at  $\leq$  -20°C the day of collection. All the aliquots of serum will be shipped on dry ice to Covance Central Laboratories (Geneva, Switzerland), where they will be biobanked for future use.

An additional volume of approximately 4 mL of peripheral blood will be collected in a similar fashion at each time point (see above and Section 1-2) for RTX immunogenicity assessment and monitoring of RTX concentration in serum (see Section 9.3). Serum samples will be isolated, aliquoted and frozen on site at ≤-20°C the day of collection. All serum aliquots will be shipped on dry ice to Covance Central Laboratories (Geneva, Switzerland), where they will be biobanked for future use.

Instructions for handling procedures, preparation, storage and shipping of the serum samples will be provided in the study laboratory manual.

